### 2. Qualitative and quantitative composition

Each film-coated tablet contains 15 mg rivaroxaban.

Excipients with known effect:

Each 15 mg film-coated tablet contains 25.4 mg lactose monohydrate, see section 4.4.

For the full list of excipients, see section 6.1.

### 3. Pharmaceutical form

Film-coated tablet (tablet).

Red, round biconvex tablets (6 mm diameter, 9 mm radius of curvature) marked with the BAYER-cross on one side and "15" and a triangle on the other side.

### 4. Clinical particulars

#### 4.1 Therapeutic indications

Prevention of stroke and systemic embolism in adult patients with non-valvular atrial fibrillation with one or more risk factors, such as congestive heart failure, hypertension, age  $\geq$  75 years, diabetes mellitus, prior stroke or transient ischaemic attack.

Treatment of deep vein thrombosis (DVT), and prevention of recurrent DVT and pulmonary embolism (PE) following an acute DVT in adults.

#### 4.2 Posology and method of administration

Posology

Prevention of stroke and systemic embolism

The recommended dose is 20 mg once daily, which is also the recommended maximum dose.

Therapy with Xarelto should be continued long term provided the benefit of prevention of stroke and systemic embolism outweighs the risk of bleeding (see section 4.4).

If a dose is missed the patient should take Xarelto immediately and continue on the following day with the once daily intake as recommended. The dose should not be doubled within the same day to make up for a missed dose.

Treatment of DVT and prevention of recurrent DVT and PE

The recommended dose for the initial treatment of acute DVT is 15 mg twice daily for the first three weeks followed by 20 mg once daily for the continued treatment and prevention of recurrent DVT and PE, as indicated in the table below.

	Dosing schedule	Maximum daily dose
Day 1 - 21	15 mg twice daily	30 mg
Day 22 and onwards	20 mg once daily	20 mg

The duration of therapy should be individualised after careful assessment of the treatment benefit against the risk for bleeding (see section 4.4). Short duration of therapy (3 months) should be based on transient risk factors (e.g. recent surgery, trauma, immobilisation) and longer durations should be based on permanent risk factors or idiopathic DVT. Experience with Xarelto in this indication for more than 12 months is limited.

If a dose is missed during the 15 mg twice daily treatment phase (day 1 - 21), the patient should take Xarelto immediately to ensure intake of 30 mg Xarelto per day. In this case two 15 mg tablets may be taken at once. The patient should continue with the regular 15 mg twice daily intake as recommended on the following day.

If a dose is missed during the once daily treatment phase (day 22 and onwards), the patient should take Xarelto immediately, and continue on the following day with the once daily intake as recommended. The dose should not be doubled within the same day to make up for a missed dose.

#### Converting from Vitamin K Antagonists (VKA) to Xarelto

For patients treated for prevention of stroke and systemic embolism, VKA treatment should be stopped and Xarelto therapy should be initiated when the INR is  $\leq$  3.0.

For patients treated for DVT and prevention of recurrent DVT and PE, VKA treatment should be stopped and Xarelto therapy should be initiated once the INR is  $\leq 2.5$ .

When converting patients from VKAs to Xarelto, INR values will be falsely elevated after the intake of Xarelto. The INR is not valid to measure the anticoagulant activity of Xarelto, and therefore should not be used (see section 4.5).

Converting from Xarelto to Vitamin K antagonists (VKA)

There is a potential for inadequate anticoagulation during the transition from Xarelto to VKA. Continuous adequate anticoagulation should be ensured during any transition to an alternate anticoagulant. It should be noted that Xarelto can contribute to an elevated INR.

In patients converting from Xarelto to VKA, VKA should be given concurrently until the INR is  $\geq$  2.0. For the first two days of the conversion period, standard initial dosing of VKA should be used followed by VKA dosing guided by INR testing. While patients are on both Xarelto and VKA the INR should not be tested earlier than 24 hours after the previous dose but prior to the next dose of Xarelto. Once Xarelto is discontinued INR testing may be done reliably at least 24 hours after the last dose (see sections 4.5 and 5.2).

Converting from parenteral anticoagulants to Xarelto

For patients currently receiving a parenteral anticoagulant, Xarelto should be started 0 to 2 hours before the time of the next scheduled administration of the parenteral medicinal product (e.g. LMWH) or at the time of discontinuation of a continuously administered parenteral medicinal product (e.g. intravenous unfractionated heparin).

Converting from Xarelto to parenteral anticoagulants

Give the first dose of parenteral anticoagulant at the time the next Xarelto dose would be taken.

#### Special populations

Renal impairment

No dose adjustment is necessary in patients with mild renal impairment (creatinine clearance 50 - 80 ml/min) (see section 5.2).

In patients with moderate (creatinine clearance 30 - 49 ml/min) or severe (creatinine clearance 15 - 29 ml/min) renal impairment the following dosage recommendations apply:

- For the prevention of stroke and systemic embolism in patients with non-valvular atrial fibrillation, the recommended dose is 15 mg once daily (see section 5.2).

- For the treatment of DVT and prevention of recurrent DVT and PE: Patients should be treated with 15 mg twice daily for the first 3 weeks. Thereafter, the recommended dose is 15 mg once daily based on PK modelling (see sections 4.4 and 5.2).

Limited clinical data for patients with severe renal impairment (creatinine clearance 15 - 29 ml/min) indicate that rivaroxaban plasma concentrations are significantly increased, therefore, Xarelto is to be used with caution in these patients. Use is not recommended in patients with creatinine clearance < 15 ml/min (see sections 4.4 and 5.2).

### Hepatic impairment

Xarelto is contraindicated in patients with hepatic disease associated with coagulopathy and clinically relevant bleeding risk including cirrhotic patients with Child Pugh B and C (see sections 4.3 and 5.2).

#### Elderly population

No dose adjustment (see section 5.2).

Body weight

No dose adjustment (see section 5.2).

Gender

No dose adjustment (see section 5.2).

### Paediatric population

The safety and efficacy of Xarelto in children aged 0 to 18 years have not been established. No data are available. Therefore, Xarelto is not recommended for use in children below 18 years of age.

#### Method of administration

For oral use. The tablets are to be taken with food (see section 5.2).

#### 4.3 Contraindications

Hypersensitivity to the active substance or to any of the excipients listed in section 6.1.

Clinically significant active bleeding.

Hepatic disease associated with coagulopathy and clinically relevant bleeding risk including cirrhotic patients with Child Pugh B and C (see section 5.2).

Pregnancy and breast feeding (see section 4.6).

### 4.4 Special warnings and precautions for use

Clinical surveillance in line with anticoagulation practice is recommended throughout the treatment period.

Haemorrhagic risk

In the clinical studies mucosal bleedings (i.e. epistaxis, gingival, gastrointestinal, genito urinary) and anemia were seen more frequently during long term rivaroxaban treatment compared with VKA treatment. Thus, in addition to adequate clinical surveillance, laboratory testing of haemoglobin/haematocrit could be of value to detect occult bleeding, as judged to be appropriate.

Several sub-groups of patients, as detailed below, are at increased risk of bleeding. These patients are to be carefully monitored for signs and symptoms of bleeding complications and anaemia after initiation of treatment (see section 4.8).

Any unexplained fall in haemoglobin or blood pressure should lead to a search for a bleeding site.

#### Renal impairment

In patients with severe renal impairment (creatinine clearance < 30 ml/min) rivaroxaban plasma levels may be significantly increased (1.6 fold on average) which may lead to an increased bleeding risk. Xarelto is to be used with caution in patients with creatinine clearance 15 - 29 ml/min. Use is not recommended in patients with creatinine clearance < 15 ml/min (see sections 4.2 and 5.2).

Xarelto should be used with caution in patients with renal impairment concomitantly receiving other medicinal products that are potent inhibitors of CYP3A4 (e.g. clarithromycin, telithromycin) as PK modelling shows increased rivaroxaban concentrations in these patients.

#### Interaction with other medicinal products

The use of Xarelto is not recommended in patients receiving concomitant systemic treatment with azole-antimycotics (such as ketoconazole, itraconazole, voriconazole and posaconazole) or HIV protease inhibitors (e.g. ritonavir). These active substances are strong inhibitors of both CYP3A4 and P-gp and therefore may increase rivaroxaban plasma concentrations to a clinically relevant degree (2.6 fold on average) which may lead to an increased bleeding risk (see section 4.5).

Care is to be taken if patients are treated concomitantly with medicinal products affecting haemostasis such as non-steroidal anti-inflammatory medicinal products (NSAIDs), acetylsalicylic acid, platelet aggregation inhibitors or other antithrombotic agents. For patients at risk of ulcerative gastrointestinal disease an appropriate prophylactic treatment may be considered (see section 4.5).

Other haemorrhagic risk factors

Rivaroxaban, like other antithrombotic agents, is to be used with caution in patients with an increased bleeding risk such as:

- · congenital or acquired bleeding disorders
- uncontrolled severe arterial hypertension
- · active ulcerative gastrointestinal disease
- recent gastrointestinal ulcerations
- · vascular retinopathy
- · recent intracranial or intracerebral haemorrhage
- · intraspinal or intracerebral vascular abnormalities
- · recent brain, spinal or ophthalmological surgery
- · bronchiectasis or history of pulmonary bleeding.

There is no need for monitoring of coagulation parameters during treatment with rivaroxaban in clinical routine. However, if clinically indicated rivaroxaban levels can be measured by calibrated quantitative anti-Factor Xa tests (see section 5.1 and 5.2).

### Patients with prosthetic valves

Safety and efficacy of Xarelto have not been studied in patients with prosthetic heart valves; therefore, there are no data to support that Xarelto 20 mg (15 mg in patients with moderate or severe renal impairment) provides adequate anticoagulation in this patient population. Treatment with Xarelto is not recommended for these patients.

Patients with acute pulmonary embolism

Xarelto is not recommended in the treatment of acute pulmonary embolism.

#### Dosing recommendations before and after invasive procedures and surgical intervention

If an invasive procedure or surgical intervention is required, Xarelto should be stopped at least 24 hours before the intervention, if possible and based on the clinical judgement of the physician.

If the procedure cannot be delayed the increased risk of bleeding should be assessed against the urgency of the intervention.

Xarelto should be restarted after the invasive procedure or surgical intervention as soon as possible provided the clinical situation allows and adequate haemostasis has been established (see section 5.2).

#### Information about excipients

Xarelto contains lactose. Patients with rare hereditary problems of galactose intolerance, the Lapp lactase deficiency or glucose-galactose malabsorption should not take this medicinal product.

#### 4.5 Interaction with other medicinal products and other forms of interaction

CYP3A4 and P-gp inhibitors

Co-administration of rivaroxaban with ketoconazole (400 mg once a day) or ritonavir (600 mg twice a day) led to a 2.6 fold / 2.5 fold increase in mean rivaroxaban AUC and a 1.7 fold / 1.6 fold increase in mean rivaroxaban  $C_{max}$ , with significant increases in pharmacodynamic effects which may lead to an increased bleeding risk. Therefore, the use of Xarelto is not recommended in patients receiving concomitant systemic treatment with azole-antimycotics such as ketoconazole, itraconazole, voriconazole and posaconazole or HIV protease inhibitors. These active substances

are strong inhibitors of both CYP3A4 and P-gp (see section 4.4).

Active substances strongly inhibiting only one of the rivaroxaban elimination pathways, either CYP3A4 or P-gp, are expected to increase rivaroxaban plasma concentrations to a lesser extent. Clarithromycin (500 mg twice a day), for instance, considered as a strong CYP3A4 inhibitor and moderate P-gp inhibitor, led to a 1.5 fold increase in mean rivaroxaban AUC and a 1.4 fold increase in  $C_{max}$ . This increase is not considered clinically relevant.

Erythromycin (500 mg three times a day), which inhibits CYP3A4 and P-gp moderately, led to a 1.3 fold increase in mean rivaroxaban AUC and  $C_{max}$ . This increase is not considered clinically relevant.

Fluconazole (400 mg once daily), considered as a moderate CYP3A4 inhibitor, led to a 1.4 fold increase in mean rivaroxaban AUC and a 1.3 fold increase in mean Cmax. This increase is not considered clinically relevant.

Given the limited clinical data available with dronedarone, co-administration with rivaroxaban should be avoided.

#### Anticoagulants

After combined administration of enoxaparin (40 mg single dose) with rivaroxaban (10 mg single dose) an additive effect on anti-Factor Xa activity was observed without any additional effects on clotting tests (PT, aPTT). Enoxaparin did not affect the pharmacokinetics of rivaroxaban.

Due to the increased bleeding risk care is to be taken if patients are treated concomitantly with any other anticoagulants (see section 4.4).

### NSAIDs/platelet aggregation inhibitors

No clinically relevant prolongation of bleeding time was observed after concomitant administration of rivaroxaban (15 mg) and 500 mg naproxen. Nevertheless, there may be individuals with a more pronounced pharmacodynamic response.

No clinically significant pharmacokinetic or pharmacodynamic interactions were observed when rivaroxaban was co-administered with 500 mg acetylsalicylic acid.

Clopidogrel (300 mg loading dose followed by 75 mg maintenance dose) did not show a pharmacokinetic interaction with rivaroxaban (15 mg) but a relevant increase in bleeding time was observed in a subset of patients which was not correlated to platelet aggregation, P-selectin or GPIIb/IIIa receptor levels.

Care is to be taken if patients are treated concomitantly with NSAIDs (including acetylsalicylic acid) and platelet aggregation inhibitors because these medicinal products typically increase the bleeding risk (see section 4.4).

#### Warfarin

Converting patients from the vitamin K antagonist warfarin (INR 2.0 to 3.0) to rivaroxaban (20 mg) or from rivaroxaban (20 mg) to warfarin (INR 2.0 to 3.0) increased prothrombin time/INR (Neoplastin) more than additively (individual INR values up to 12 may be observed), whereas effects on aPTT, inhibition of factor Xa activity and endogenous thrombin potential were additive.

If it is desired to test the pharmacodynamic effects of rivaroxaban during the conversion period, anti-factor Xa activity, PiCT, and Heptest can be used as these tests were not affected by warfarin. On the fourth day after the last dose of warfarin, all tests (including PT, aPTT, inhibition of factor Xa activity and ETP) reflected only the effect of rivaroxaban.

If it is desired to test the pharmacodynamic effects of warfarin during the conversion period, INR measurement can be used at the Ctrough of rivaroxaban (24 hours after the previous intake of rivaroxaban) as this test is minimally affected by rivaroxaban at this time point.

No pharmacokinetic interaction was observed between warfarin and rivaroxaban.

## CYP3A4 inducers

Co-administration of rivaroxaban with the strong CYP3A4 inducer rifampicin led to an approximate 50 % decrease in mean rivaroxaban AUC, with parallel decreases in its pharmacodynamic effects. The concomitant use of rivaroxaban with other strong CYP3A4 inducers (e.g. phenytoin,

carbamazepine, phenobarbital or St. John's Wort) may also lead to reduced rivaroxaban plasma concentrations. Strong CYP3A4 inducers should be co-administered with caution.

## Other concomitant therapies

No clinically significant pharmacokinetic or pharmacodynamic interactions were observed when rivaroxaban was co-administered with midazolam (substrate of CYP3A4), digoxin (substrate of P-gp), atorvastatin (substrate of CYP3A4 and P-gp) or omeprazole (proton pump inhibitor). Rivaroxaban neither inhibits nor induces any major CYP isoforms like CYP3A4.

#### Laboratory parameters

Clotting parameters (e.g. PT, aPTT, HepTest) are affected as expected by the mode of action of rivaroxaban (see section 5.1).

#### 4.6 fertility, pregnancy and breast feeding

Pregnancy

Safety and efficacy of Xarelto have not been established in pregnant women. Studies in animals have shown reproductive toxicity (see section 5.3). Due to the potential reproductive toxicity, the intrinsic risk of bleeding and the evidence that rivaroxaban passes the placenta, Xarelto is contraindicated during pregnancy (see section 4.3).

Women of child-bearing potential should avoid becoming pregnant during treatment with rivaroxaban.

### Breast feeding

Safety and efficacy of Xarelto have not been established in breast feeding women. Data from animals indicate that rivaroxaban is secreted into milk. Therefore Xarelto is contraindicated during breast feeding (see section 4.3). A decision must be made whether to discontinue breast feeding or to discontinue/abstain from therapy.

### Fertility

No specific studies with rivaroxaban in humans have been conducted to evaluate effects on fertility. In a study on male and female fertility in rats no effects were seen (see section 5.3).

### 4.7 Effects on ability to drive and use machines

Xarelto has minor influence on the ability to drive and use machines. Adverse reactions like syncope and dizziness have been reported to be common (see section 4.8). Patients experiencing these adverse reactions should not drive or use machines.

## 4.8 Undesirable effects

Summary of the safety profile

The safety of rivaroxaban has been evaluated in eight phase III studies including 16,041 patients exposed to rivaroxaban (see Table 1).

### Table 1: Number of patients studied, maximum daily dose and treatment duration in phase III studies

Indication	Number of patients*	Maximum daily dose	Maximum treatment duration
Prevention of venous thromboembolism (VTE) in adult patients undergoing elective hip or knee replacement surgery	6,097	10 mg	39 days
Treatment of DVT and prevention of recurrent DVT and PE	2,194	Day 1 - 21: 30 mg Day 22 and onwards: 20 mg	21 months
Prevention of stroke and systemic embolism in patients with non-valvular atrial fibrillation	7,750	20 mg	41 months

\*Patients exposed to at least one dose of rivaroxaban

In total about 73% of patients exposed to at least one dose of rivaroxaban were reported with treatment emergent adverse events. About 24% of the patients experienced adverse events considered related to treatment as assessed by investigators. In patients treated with 10 mg Xarelto undergoing hip or knee replacement surgery, bleeding events occurred in approximately 6.8% of patients and anaemia occurred in approximately 5.9% of patients. In patients treated with either 15 mg twice daily Xarelto followed by 20 mg once daily for treatment of DVT, or with 20 mg once daily for prevention of recurrent DVT and PE, bleeding events occurred in approximately 22.7% of patients and anaemia occurred in approximately 1.8% of patients. In patients treated for prevention of stroke and systemic embolism, bleeding of any type or severity was reported with an event rate of 28 per 100 patient years, and anaemia with an event rate of 2.5 per 100 patient years.

Tabulated list of adverse reactions

The frequencies of adverse reactions reported with Xarelto are summarised in table 2 below by system organ class (in MedDRA) and by frequency.

Frequencies are defined as:

common ( $\geq 1/100$  to < 1/10)

uncommon ( $\geq 1/1,000$  to < 1/100)

rare (≥ 1/10,000 to < 1/1,000)

Not known: cannot be estimated from the available data.

Table 2: All treatment-emergent adverse reactions reported in patients in phase III studies (prevention of venous thromboembolism (VTE) in adult patients undergoing elective hip or knee replacement surgery (*VTE-P*), treatment of DVT and prevention of recurrent DVT and PE (*DVT-T*), and prevention of stroke and systemic embolism in patients with non-valvular atrial fibrillation (*SPAF*))

Common	Uncommon	Rare	Not known
Blood and lymphatic system dis	orders		1
Anaemia (incl. respective	Thrombocythemia (incl. platelet		
laboratory parameters)	count increased) A		
Immune system disorders	·		
	Allergic reaction, dermatitis		
	allergic		
Nervous system disorders			1
Dizziness, headache, syncope	Cerebral and intracranial		
	haemorrhage		
Eye disorders		1	1
Eye haemorrhage (incl.			
conjunctival haemorrhage)			
Cardiac disorders		·	-
Tachycardia			
Vascular disorders	·		
Hypotension, haematoma			Pseudoaneurysm formation
			following percutaneous
			intervention*
Respiratory, thoracic and medi	astinal disorders		
Epistaxis	Haemoptysis		
Gastrointestinal disorders	-		

Gastrointestinal tract haemorrhage	Dry mouth		
(incl. gingival bleeding and rectal			
haemorrhage), gastrointestinal and			
abdominal pains, dyspepsia,			
nausea, constipation A , diarrhoea,			
vomiting A			
Hepatobiliary disorders	1	1	1
	Hepatic function abnormal	Jaundice	
Skin and subcutaneous tissue disc	orders	1	
Pruritus (incl. uncommon cases of	Urticaria, cutaneous and		
generalised pruritus), rash,	subcutaneous haemorrhage		
ecchymosis			
Musculoskeletal and connective t	issue disorders		
	····		
Pain in extremity A	Haemarthrosis	Muscle haemorrhage	Compartment syndrome
			secondary to a bleeding
Renal and urinary disorders			
Urogenital tract haemorrhage	Renal impairment (incl. blood		Renal failure/acute renal
(incl. haematuria and	creatinine increased, blood urea		failure secondary to a
menorrhagia B )	increased) A		bleeding sufficient to cause
			hypoperfusion
General disorders and administra	ation site conditions	1	
Fever A , peripheral oedema,	Feeling unwell (incl. malaise),		
decreased general strength and	localised oedema A		
energy (incl. fatigue and asthenia)			
Investigations	1	1	
Increase in transaminases	Increased bilirubin, increased	Bilirubin conjugated increased	
	blood alkaline phosphatase A ,	(with or without concomitant	
	increased LDH A , increased	increase of ALT)	
	lipase A , increased amylase A ,		
	increased GGT A		
Injury, poisoning and procedural	complications	1	1
Postprocedural haemorrhage (incl.			
postoperative anaemia, and wound			
haemorrhage), contusion, wound			
secretion A			
haemorrhage), contusion, wound			

A: observed in VTE-P after major orthopaedic surgery of the lower limbs

B: observed in DVT-T as very common in women < 55 years

\*) These reactions ocurred in other clinical studies than the phase III studies in patients undergoing major orthopaedic surgery of the lower limbs, patients treated for DVT and prevention of recurrent DVT and PE, or patients treated for the prevention of stroke and systemic embolism

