- Patients receiving concomitant systemic treatment with CYP3A4 or P-gp inhibitors other than azole antimycotics (e.g. ketoconazole) and HIV protease inhibitors (e.g. ritonavir)
- Remedial pro-coagulant therapy for excessive haemorrhage
- Pregnant or breast-feeding women
- Patients with AF and a prosthetic heart valve
- long term therapy with rivaroxaban in treatment of DVT, PE and SPAF in real-life setting.
- $\circ$  Patients < 18 years

Outcomes of special interest

- Increase in liver enzymes [alanine aminotransferase (ALT), aspartate aminotransferase (AST)], Gamma-Glutamyl Transferase (GGT)] and bilirubin
- Management of homeostasis in patients with the indications of interest who also undergo surgery (elective or urgent) during the observation period in this study.

The safety profile and efficacy of rivaroxaban in children aged <18 years have not been established. No data are available. Therefore, rivaroxaban is not recommended for use in children below 18 years of age. [1] A Paediatric Investigation Plan (PIP) has been agreed with EMA, the aim of which is to contribute to the insight in the efficacy and safety profile of rivaroxaban in paediatric populations.

Off label prescribing of rivaroxaban (in terms of medical indication, dose etc) is possible so any data relating to off label use will be examined in this study.

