## 2.2.2 Secondary Objectives

These are given below. Their purpose is to provide timely information on:

Version 40 20/11/2014 REC Ref 12/SC/0592

(i) Prescriber and cohort accrual and the type of prescriber responsible for, and the setting of initiation of treatment with either rivaroxaban or alternative anticoagulant therapy.

(ii) Prevalence of non-clinical reasons for prescribing, prognostic health factors and clinical risk factors for haemorrhage as reported in medical charts for patients undergoing anticoagulation with either rivaroxaban or alternative anticoagulant therapy in the secondary care hospital setting and the treatment programme they received to advance the understanding of the patient population prescribed rivaroxaban in actual clinical practice in the secondary care hospital setting

(iii) Changes of health profile of patients, assessment of adherence, plus any alterations of the treatment programme during the 12 week observation period, as recorded in medical charts.(iv) To quantify the risk of:

(a) (separately) haemorrhage within gastrointestinal and urogenital organ sites (which meets the criteria for a major bleed) and all intracranial sites for contextual anticoagulant therapy cohort

(b) all major bleeding specified in primary objective for both rivaroxaban and contextual anticoagulant therapy cohort (as composite)

(c) (separately) haemorrhage (major bleeding according to Table 2) within critical organ sites other than specified in primary objective for both rivaroxaban and contextual anticoagulant therapy cohort

(d) all major and clinically relevant non-major bleeds (as a composite outcome)

(e) thromboembolic complications (incident and recurrent)

(f) other†† events including special outcomes of interest (severe hepatic failure and abnormal LFTs above 3x ULN) as recorded in medical charts during the 12 week observation period and, if number of reports are sufficient, in patient subgroups of special interest, including:

- reported indications
- elderly (>= 65 years)‡‡, other contraindicated or special groups (e.g. pregnant and breastfeeding women, patients with concurrent significant renal or hepatic impairment; patients with known VTE and/or haemorrhagic risk factors e.g. congenital or acquired bleeding disorders, uncontrolled severe arterial

<sup>†† Other than major and clinically relevant non major bleeding outcomes, or thromboembolic complications (recurrent or incident)

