## 4.4.2.2 Eligible patient index date information

For all eligible patients invited to participate, the following anonymised information will be collected using information contained within medical charts.

- o demographic characteristics (age, gender)
- Reasons for prescribing (clinical judgement, recommendation from NICE, expert committee guidelines, trust formulary committee guidelines, Patient Group Direction in anticoagulation clinic, potential ease of reversibility of anticoagulant, lifestyle

(anticoagulant monitoring needs), patient non-adherence with prior anticoagulant therapy, side-effects with prior anticoagulant therapy.

- $\circ$  which anticoagulant regimen was prescribed and start date
- o clinical condition requiring anticoagulation (indication)
- Prior anticoagulation treatment
- Stroke and Bleeding risk factors
  - Congestive Heart Failure/Left Ventricular Dysfunction
  - o TIA/Thromboembolism History
  - Previous History of Stroke
  - Vascular Disease History (previous MI, peripheral arterial disease or aortic plaque)
  - History of Hypertension
  - Current Hypertension
  - Uncontrolled BP, > 160mmhHg systolic at time of treatment initiation
  - o Medication Usage Predisposing to Bleeding (Antiplatelet agents, NSAIDs
  - Labile INR (Unstable/high INRs)
  - Diabetes Mellitus
  - Alcohol Abuse or Excess†††††
  - ο Renal Disease (Dialysis, transplant, Cr >200 μmol/L)
  - Abnormal Liver Function (Cirrhosis, Bilirubin >2x Normal, AST/ALT/ALP >3x Normal)
  - Prior Major Bleeding or Predisposition to Bleeding

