Management of homeostasis	Targeted outcome question	Data on management of homeostasis in
		patients reported with events of surgery
		(elective or urgent ) during the observation
Increased liver transaminases and Gamma-	Terreted outcome supption	period will be collected via follow-up
	Targeted outcome question	Data on diagnosis of hepatic failure and where abnormal laboratory results indicate 3
Glutamyl Transferase (GGT)		
		X ULN relevant parameters will be collected via follow-up.
Concomitant use of contraindicated	Targeted outcome question on	Further data may be collected via follow-up
medications and medications to be used with	other medications to gather	i uniner data may be collected via follow-up
caution	duration and changes	
IMPORTANT MISSING INFORMATION for general		
Use during pregnancy and lactation	General event report	Further data to be collected via follow-up
use during pregnancy and lactation		i urtiler uata to be collected via ioliow-up

Table 4.	Selected	events o	f interest	requiring	further	evaluation
I abit T.	Sciette	CVCIILS U	1 mici csi	requiring	i ui uici	cvaluation

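### Bilirubin is a named outcome of special interest, but the targeted liver item covers only transaminases and GGT, so isolated bilirubin rises are not actively solicited and are likely to be under-ascertained

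*Supplement*

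**What the plan says.** Section 1.3.2 sets out the outcome of special interest as "Increase in liver enzymes [alanine aminotransferase (ALT), aspartate aminotransferase (AST)], Gamma-Glutamyl Transferase (GGT)] and bilirubin". It gives no threshold.

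Secondary objective (iv)(f) in section 2.2.2 turns the liver outcome into "severe hepatic failure and abnormal LFTs above 3x ULN" and does not say which tests count.

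Table 4 (section 4.4.2.3) lists what is to be collected by targeted question. Its liver row is headed "Increased liver transaminases and Gamma"-glutamyl transferase. The comment column says that follow-up covers hepatic failure and cases "where abnormal laboratory results indicate 3" "X ULN relevant parameters will be collected". The relevant parameters are not listed.

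Elsewhere on the 12-week form, the laboratory item gives haemoglobin, platelets and clotting as its parameters. The hepatic item concerns disorders present at index and recent abnormal liver tests. The abridged GP form (section 4.4.2.4) takes its event item from Table 4.

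The appended 15 mg label (section 4.8, Table 2, Investigations) lists increased bilirubin as uncommon. It lists "Bilirubin conjugated increased", with or without a rise in ALT, as rare.

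**The concern.** Table 4 exists so that the special outcomes do not depend on a reporter judging a result worth writing down. Four analytes are named in the safety specification and three reach the table. If the forms follow the table, a bilirubin rise with normal transaminases and GGT is never prompted for.

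Two things are at stake. The first is the frequency of a named outcome, which would lean towards under-counting. The second is whether the report can separate a bilirubin rise that accompanies a transaminase rise from one that stands alone, a distinction that the label itself draws. Section 4.1 expects care to be shared with the GP for most patients and uses the GP form to limit under-reporting, so an omission in Table 4 passes into that form too.

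**Working it through.** **Comparison of the listed items.** The protocol states no figure on this point, so the main check sets the passages side by side.

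| Place | ALT/AST | GGT | Bilirubin |
|---|---|---|---|
| 1.3.2, outcome of special interest | named | named | named |
| 2.2.2 (iv)(f), objective | generic liver tests | generic | generic |
| Table 4, targeted row | named | named | not named |
| 4.4.2.3, listed laboratory parameters | not named | not named | not named |
| 4.4.2.3, hepatic item | index disorders and recent tests | same | same |
| 4.4.2.4, GP form event item | via Table 4 | via Table 4 | not via Table 4 |

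The adjacent renal item in 4.4.2.3 asks for status at index and for change over the 12 weeks. The hepatic item makes no such request for change. Bilirubin is thus the only one of the four analytes with no named on-treatment prompt.

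**Can transaminases or GGT stand in for it?** The label reports conjugated bilirubin rises with or without an ALT rise, so not reliably.

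**Scale, as context only.** Inputs: 1700 rivaroxaban patients (section 4.2); label bands of uncommon, 1/1,000 to below 1/100, and rare, 1/10,000 to below 1/1,000.

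The method is first checked against the protocol's own surveillance figure in section 4.2.2: P(X ≥ 3) = 1 − P(X ≤ 2), with X binomial (1700, 1/200). The result is 0.991, which reproduces the stated 99%.

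Expected cases = 1700 × rate, assuming that every case is captured:

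- Any bilirubin rise (uncommon): 1700 × 0.001 = 1.7 to 1700 × 0.01 = 17. P(at least 3) runs from 0.24 to above 0.999.
- Conjugated bilirubin rise (rare): 1700 × 0.0001 = 0.17 to 1700 × 0.001 = 1.7. P(at least 3) runs from 0.0007 to 0.24.

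The documents give no capture rate. Assuming 25% to 75% capture, so that the rate becomes band rate × capture:

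- At 1/1,000, P(at least 3) falls from 0.24 to between 0.009 and 0.14.
- At 1/100, it lies between 0.80 and above 0.999.

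Incomplete capture therefore matters most near the lower end of the uncommon band. For the rare band the study would seldom see three cases even with full capture.

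**The case against.** The strongest reply is that other routes exist. The event definition in the Executive Summary takes in clinically important laboratory changes. The 12-week laboratory item opens with a general reference to relevant parameters and notes that abnormalities are reported as events. Free text is coded and analysed (sections 4.5.2 and 4.7.5). Jaundice, hepatitis and hepatic failure are on the Appendix 2 list for automatic follow-up, unless a more likely explanation is given (section 4.4.2.5). The questionnaire is not shown, and neither the generic liver tests in (iv)(f) nor the unlisted follow-up parameters exclude bilirubin. All of this stands. It rules out saying that such rises are missed, or that a transaminase rise could never be paired with a bilirubin value. It does not supply a prompt: free text depends on the reporter's judgement, and the Appendix 2 entries are clinical diagnoses, not laboratory rises.

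Three stronger readings are tempting and are not supported:

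- *A bias from two cut-offs.* The index form has "Abnormal Liver Function (Cirrhosis, Bilirubin >2x Normal, AST/ALT/ALP >3x Normal"), while the outcome is 3x ULN. But the index item sits in the list of stroke and bleeding risk factors, and section 4.7.4 names no comparison of liver tests between index and 12 weeks. A different cut-off for an outcome and for a risk factor is not a bias in itself. Nor does the label list rises of 2 to 3 times normal; it gives no multiple.
- *GGT as the wrong target.* The label footnotes raised GGT with "A: observed in VTE-P after major orthopaedic surgery of the lower limbs", a setting outside this study. Section 1.3.2 nonetheless names GGT, so collecting it is no error.
- *1.7 to 17 cases lost.* That range counts any bilirubin rise. Its source pools populations treated for at most 39 days to 41 months, and 6,097 of the 16,041 patients (38%) were surgical.

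**Conclusion.** The point holds as a gap between a named outcome and its data collection. Bilirubin is in section 1.3.2, is absent from the Table 4 liver row, and has no other listed on-treatment prompt on either form. Bilirubin rises without a transaminase or GGT rise are therefore not actively solicited and are likely to be under-ascertained, with partial capture through free text and diagnosed liver disease.

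The number affected cannot be derived from the documents. The conclusion assumes that the forms follow the wording of Table 4; if the actual question already includes bilirubin, only the protocol text needs correcting. The effect is confined to one component of secondary objective (iv)(f) and leaves the primary haemorrhage outcome untouched. It is still worth changing, because the omission concerns an outcome that the protocol itself singles out.

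**What to change.** 1. Add bilirubin (total, and conjugated where recorded) to the Table 4 liver row and to the targeted liver question on the 12-week specialist form and the abridged GP form.
2. In objective (iv)(f), name the analytes and state the outcome threshold for each, and list the parameters to be collected at follow-up in Table 4.
3. Report bilirubin rises separately, with and without a concurrent transaminase rise.

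The cost is one more field to abstract from charts already under review, with matching edits to the table and objective. No extra tests or visits are needed.
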